### ***9.1.10. Medication Re-Introduction for Subjects with 3M Systolic OBP $\geq$ 140 mm Hg***

Upon completion of a valid ABPM at the 3-month follow-up visit, subjects with an office SBP<140 mmHg do not need to be followed up for study purposes until the 6-month follow-up visit. Subjects with an office SBP  $\geq$  140 mmHg will begin an antihypertensive medication regimen of one or more of the following classes individually or in a combination pill with dosing at the discretion of the study investigator:

- ACE/ARB
- Calcium Channel Blocker
- Thiazide-Type Diuretic

Subjects will return at 4 months ( $\pm 7$  days) to perform a clinical assessment and obtain an Office Blood Pressure according to the guidelines in **Appendix 16.5**.

- The investigator may utilize his or her discretion in modifying the antihypertensive regimen.
- Any modification to the anti-hypertensive medication regimen must be documented on the CRFs.

To provide the appropriate oversight for study subjects, the visit schedule between the required 4-month and 6-month visits may need to be adapted to account for a subject's clinical status, complexity of the medication regimen, and/or the subject's blood pressure. If additional changes to the anti-hypertensive medication regimen are made between 3 and up to 6 months post-procedure, complete an unscheduled follow-up visit, and obtain an OPB according to the guidelines in **Appendix 16.5**. In addition, all medication changes are to be documented on the CRF. All medication used should be commercially available in the respective geographies and compliant with local labeling.

Table 3: Schedule of Treatments and Assessments

Required Assessments	Screening			Procedure		Post-procedure follow up								
	SV1	2Wk	SV2	Proced ure	DC	2Wk	1M	6Wk	8Wk	10Wk	3M	4M	6M	12M
Mode (O- in office, P-phone)	O	O	O			O	O	P 	P 	P 	O	O	O	O
Window (M-month, Wk-week, d-days)	--	±3 d			--	±3 d	±7 d	±3 d	±7 d	±3 d	±14 d	±7 d	±14 d	±30 d
Medical history	X													
Clinical assessment		X	X			X	X				X	X 	X 	X 
Renal denervation procedure				X										
OBP per study guidelines	X	X	X		X	X	X	X 	X 	X 	X	X	X	X
24h ABPM per study guidelines			X								X		X	X
Witnessed pill intake 													X	X
Medications prescribed 												X 		
Blood tests (Chem7) 			X		X		X				X		X	X
Serum or urine pregnancy test			X											
Drug testing			X								X			
Renal artery imaging– angiogram				X										
Renal artery imaging-DUS 													X	
Mortality assessment 						X	X	X	X	X	X	X	X	X
Medication and event review	X	X	X	X	X	X	X	X	X	X	X	X	X	X 

1: 4M follow-up is only required if 3M systolic OBP $\geq$ 140 mmHg, prescribe AH medications according to **section 9.1.9** if SBP  $\geq$  140 mmHg

2: If medically necessary, phone contact may be replaced with office visit. OBP (per **Appendix 16.5**) to be obtained for an office visit or following alternative methods of data collection as described in **section 9.1.6**.

3: Witnessed pill intake (if subject is taking AH medications), complete after OBP measurements

4: Bicarbonate will not be measured for subjects enrolled in Europe.

5: DUS required as first line imaging modality at 6M. Repeat DUS, MRA, CT or angiogram to be used if DUS is nondiagnostic. Renal angiography must be used if repeat DUS/CTA/MRA is nondiagnostic or stenosis >60-70% is suspected. If renal imaging is not captured at the 6M follow-up visit due to extenuating circumstances, renal imaging is required at the next scheduled study visit.

6: Mortality assessment will be completed by the investigational site when a subject cannot be reached after each of the protocol required follow-up visits

7: SAE only review required at 12M visit

8: Clinical assessment of weight only 8: Clinical assessment of weight only

**Table 4: Schedule of testing through 12 months for subjects with office SBP  $\geq 180$  mmHg (confirmed via 2 sets of measurements) or escape via investigator discretion during off-medication period post-procedure**

Required Assessments	Procedure		Post-Procedure						
	Procedure	DC	2Wk	1M	6Wk	10Wk	3M	6M	12M
Mode (O- in office, P-phone)			O	O	O	O	O	O	O
Window (M-month, Wk-week, d-days)	--	--	$\pm 3$ d	$\pm 7$ d	$\pm 3$ d	$\pm 3$ d	$\pm 14$ d	$\pm 14$ d	$\pm 30$ d
OBP per study guidelines		X	X	X	X	X	X	X	X
Renal artery imaging 								X 	
Mortality assessment 			X	X	X	X	X	X	X
Medication and event review		X	X	X	X	X	X	X	X 

1: DUS required as first line imaging modality at 6M. Repeat DUS, MRA, CT or angiogram to be used if DUS is nondiagnostic. Renal angiography must be used if repeat DUS/CTA/MRA is nondiagnostic or stenosis >60-70% is suspected. If renal imaging is not captured at the 6M follow-up visit due to extenuating circumstances, renal imaging is required at the next scheduled study visit.

2: Mortality assessment will be completed by the investigational site when a subject cannot be reached after each of the protocol required follow-up visits

3: SAE only review required at 12M visit

## **9.2. Assessment of Safety**

Adverse event (AE) information will be collected by the site from subject enrollment (consent) through 6-months follow up. After the 6-month follow-up visit and until study termination only serious adverse events will be collected. AEs will be followed until the event has resolved (in the case of permanent impairment, the event will be followed until it stabilizes, and the overall clinical outcome has been ascertained), or subject participation in the study has ended, or study termination.

The Investigator will report any adverse events that may occur to the sponsor, and will assess seriousness, relationship (to the device, procedure, and renal denervation therapy where applicable), subsequent intervention required, resolution status and whether the adverse event resulted in the subject's discontinuation from the study. The Investigator will provide further information regarding adverse events as requested by the sponsor.

## **9.3. Recording Data**

### ***9.3.1. Database/ Case Report Forms***

Data collected on each subject will be recorded on a web-based CRF. This study will utilize an Oracle Clinical Remote Data Capture (RDC) system that is the property of Medtronic. Each enrolled subject is assigned a unique study ID number. Records of the subject/subject ID relationship will be maintained by the study site. Individual subject medical information obtained as a result of this study will be considered confidential.

Authorized site personnel as indicated on the Delegation Task List (DTL) will record the required data on CRFs. Study personnel delegated for CRF completion and/or approval per the DTL will be trained on the use of the RDC system and thereafter be provided with a username and password to access the system. Passwords are individual and cannot be shared.

The CRFs must be completed and updated to reflect the latest observations on the subjects participating in the study. The investigator (or approved sub-investigator) will electronically sign the appropriate pages of each CRF. The Oracle Clinical RDC system maintains an audit trail of entries, changes, and corrections in CRFs. If a person only authorized to complete CRFs makes changes to an already signed CRF, the investigator shall re-approve this CRF.

The hospital files (electronic or paper) will constitute source data. For the purpose of adjudication of events by the CEC, relevant event-related source documents will be redacted and collected for events that need to be adjudicated by the CEC.

The CRFs may not serve as source documents. Source documentation for data elements not routinely captured in medical records (e.g., renal angiogram variables, procedural details) may vary from center to

center. The site may use technical worksheets if identified as source documents. Worksheets need to be signed and dated by the principal investigator or a delegated investigator.

The principal investigator is responsible for ensuring that all sections of each CRF are complete and correct and that those entries can be verified against source data.

Medtronic will be responsible for the processing and quality control of the data. Data review, database cleaning and issuing and resolving data queries will be done according to Medtronic internal SOPs and the Data Management Plan for this study. The study database will employ validation programs (e.g., range and logic checks) on entered data to identify possible data entry errors and to facilitate data validation.

### **9.3.2. Blood Pressure Monitors**

The following equipment will be provided to the sites and utilized for assessing the endpoints of the study:

- Office blood pressure monitors
- 24-hour ambulatory blood pressure monitors

Medtronic will provide automated blood pressure monitors to participating centers for recording office based systolic and diastolic blood pressure through the course of the study. Blood pressure monitors will be provided to the sites for use with subjects to record ambulatory systolic and diastolic blood pressure at baseline and through subsequent follow ups. Medtronic will be responsible for the timely calibration of the monitors and replacement of monitors, in case of malfunction or failure to record accurate and reliable blood pressure data.

## **9.4. Deviation Handling**

A study deviation is defined as an event where the investigator or site personnel did not conduct the study according to the CIP, EC/IRB, applicable laws or regulations, or the investigator agreement.

Regulations require that investigators maintain accurate, complete, and current records, including documentation of any deviations from the CIP including the date of and reason for the deviation. The deviations must be reported to the sponsor on the CRF.

Investigators are not allowed to deviate from the protocol, except under emergency circumstances to protect the rights, safety, and well-being of human subjects. Investigators are required whenever possible to obtain prior approval from the Medtronic Clinical Research Department before initiating changes in or deviations from the CIP, except where necessary to protect the life or physical well-being of a subject in an emergency. Such approval will be documented in writing and maintained in the study files. Prior approval is not expected in situations where unforeseen circumstances are beyond the investigator's control (e.g., subject did not attend scheduled follow-up visit, blood sample lost by laboratory), however, the event, is still considered a deviation.

Deviations shall be reported to Medtronic regardless of whether medically justifiable, pre-approved by Medtronic, or taken to protect the subject in an emergency. Deviations to protect the life or physical wellbeing of the subject in an emergency must be reported to Medtronic and the EC/IRB within five working days.

Subject-specific deviations will be reported on the Deviation CRF. Deviations that are not subject specific (e.g., unauthorized use of an investigational device outside the study, unauthorized use of an investigational device by a physician who has not signed an investigator agreement) will be reported to Medtronic in writing. Investigators will also adhere to procedures for reporting study deviations to their EC/IRB in accordance with their EC/IRB requirements.

The investigational site's compliance with the CIP will be assessed on an ongoing basis. Corrective and preventive action plans will be developed and implemented to secure compliance. In cases of serious non-compliance, the sponsor may decide to stop subject enrollment and site participation at an investigational site based on its assessment of repeated occurrences of significant non-compliance.

Examples of deviations include but are not limited to the following:

- Failure to obtain informed consent prior to participation
- Incorrect version of the Subject Informed Consent used
- Failure to obtain EC/IRB approval before the start of the study
- Treated subject did not meet inclusion/exclusion criteria
- Follow-up visit not done
- Adverse events not reported in the required time frame as required by regulation or as specified in CIP
- Source data permanently lost
- Enrollment of subjects during lapse of EC/IRB approval

Medtronic is responsible for analyzing deviations, assessing their significance, and identifying any additional corrective and/or preventive actions (e.g. amend the CIP, additional training, terminate the study, etc.). Repetitive or serious investigator compliance issues may result in the need to initiate a corrective action plan, and in some cases freeze enrollment or ultimately terminate the investigator's participation in the clinical study. The sponsor shall consider terminating or suspending the participation of a particular investigational center or investigator in the clinical investigation if monitoring or auditing identifies serious or repeated deviations on the part of an investigator.

Medtronic will provide investigational site-specific reports to the investigators on a periodic basis summarizing information on deviations that occurred at the investigation site.

## 9.5. Reporting Requirements

### 9.5.1. Investigator Reporting Responsibilities

Report	Submitted to	Description
Adverse events	Sponsor, EC/IRB, and local Competent Authority, where applicable	Refer to Section 11.2 for reporting requirements.
Progress report	Sponsor and EC/IRB	Provide if required by local law or EC/IRB. (ISO 14155).
Withdrawal of EC/IRB approval	Sponsor	Investigator will inform Medtronic as soon as possible in case EC/IRB approval is withdrawn. In the US, the investigator must report a withdrawal of the reviewing IRB within five working days of the IRB's withdrawal.
Final report	EC/IRB (all sites), sponsor (US sites)	A copy of the Final Clinical Study Report will be provided to the EC/IRB and submitted in accordance with the EC/IRB policies and procedures. In the US, the site's final report must be submitted to the sponsor and IRB within three months after termination or completion of the investigation or the investigator's part of the investigation.
Deviations from Investigational Plan		
Planned deviation	Sponsor, EC/IRB, regulatory authority, as applicable by local regulations	Prior approval from Medtronic must always be obtained from Medtronic. If the deviation affects scientific soundness of the clinical study or the rights, safety, or welfare of the subject and is not an emergency, prior approval must be obtained from the EC/IRB and Competent Authority as applicable.

Report	Submitted to	Description
Other deviations	Sponsor, EC/IRB, regulatory authority, if applicable	
Deviations that are beyond the control of the investigator (such as subject who fails to return to follow-up visit) or deviations that do not affect the scientific soundness of the clinical study or the rights, safety, or welfare of the subject and are not an emergency, should be submitted as they are identified by the investigational site or Medtronic staff.
 
For emergency deviations to protect the life or physical wellbeing of the subject in an emergency, these must be reported to Medtronic and the EC/IRB within five working days.
 
If an investigator uses a device without obtaining subject consent, the investigator shall report such use within 5 working days after device use.

### *9.5.2. Sponsor Reporting Responsibilities*

Report	Submit to	Description
Withdrawal of EC/IRB or RA approval	EC/IRB, Investigators, and regulatory authorities, where applicable	
In case of withdrawal of EC/IRB approval Medtronic will suspend the clinical study as described below.
 
In the US, notification within 5 working days.

Premature termination or suspension of study	EC/IRB, Investigators, and regulatory authorities, where applicable	Medtronic will provide prompt notification of termination or suspension and reason(s) to investigator and where required to EC/IRB and regulatory authorities.
Progress report	IRB/EC and RAs	
This will be submitted to the IRB/EC only if required by the IRB/EC.
 
In the US, progress reports will be submitted per FDA requirements.

Report	Submit to	Description
Final report	Investigators, and regulatory authorities, where applicable	
Medtronic will provide all investigators with a copy of the final clinical study report of the clinical study.
 
EC/IRBs and regulatory authorities will be informed when required.
 

• The investigator shall have the opportunity to review and comment on the final report.

• If a clinical investigator does not agree with the final report, his/her comments shall be communicated to the other investigator(s).

 
The coordinating investigator shall sign the report. If no coordinating investigator is appointed, then the signature of the principal investigator in each study site should be obtained.

Emergency deviations from CIP	Regulatory authorities, where applicable	If required, Medtronic will inform regulatory authorities as soon as possible about any emergency deviations that affect scientific soundness of the clinical study or the rights, safety, or welfare of the subject.
Study deviation	Investigators	
Ensure that all deviations from the CIP are reviewed with the appropriate clinical investigator(s), are reported on the CRFs and the final report of the clinical investigation. (ISO 14155:2020)
 
Study site specific study deviations will be submitted to investigators periodically.

## 9.6. Subject Withdrawal or Discontinuation

### 9.6.1. Subject Exit from Study

There are many scenarios in which a subject may exit the study. **Table 5** details how the data will be handled for each scenario.

It is the subject's right to withdraw from the study at any time and for any reason without sanction, penalty, or loss of benefits to which the subject is otherwise entitled, and without jeopardizing their future medical care. The investigator may withdraw the subject at any time to protect the health, safety, or welfare of the subject. The subject's vital status should be recorded at the last point of contact (if outside a study-required visit). Every effort should be made to collect the status of any ongoing adverse events, at a minimum. The subject will not be considered lost to follow up during the course of this study.

All subjects will be encouraged to remain in the study through the last follow-up visit, including receipt of any results such as valid ABPM, labs, imaging, etc. Subjects who discontinue participation prematurely will be included in the analysis of results; but will not be replaced in the enrollment of total study subjects. If the subject discontinues participating in the study prior to completing the study requirements, the reason for withdrawal will be recorded in the subject's study records.

If withdrawal from the study is due to problems related to the investigational device safety or performance, the investigator shall ask for the subject's permission to follow the subject's status outside the clinical study.

**Table 5: Scenarios for Subject Exit from Study**

Scenario	Follow up Required
Subject enrolled (Patient Information and Informed Consent form signed), but the procedure is never attempted	None
Subject enrolled and exits the study early due to any of the following: - death - withdrawal	Through point of death, withdrawal, or last visit completed; consent to continue to allow data collection from their medical records is required
Subject enrolled, undergoes renal denervation and completes the study requirements	Through a minimum of 12 months follow up post-procedure up to a maximum of 5 years follow up post-procedure.

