- Blood tests
- Procedural angiogram (renal artery imaging – angiogram)
- Follow-up Duplex Ultrasound imaging (DUS) (renal artery imaging)

- Follow-up Magnetic Resonance imaging (MRA) (renal artery imaging)
- Follow-up Computerized Tomographic imaging (CTA) (renal artery imaging)

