### **9.1.5. Procedure Visit**

#### **9.1.5.1. Renal Angiography**

The denervation procedure will occur once all eligibility criteria have been met as evaluated at Screening Visit 2 and during the renal angiogram.

Prior to undergoing renal denervation, the key inclusion/exclusion criteria will be re-confirmed by a renal angiography to ensure that subjects still meet previously assessed eligibility criteria. When scheduled, subjects will be prepared for a renal angiography according to standard procedures. For subjects with chronic kidney disease and/or other risk factors for contrast-induced nephropathy (CIN), the hospital's standard-of-care protocol for CIN prevention will be used. Prior to this procedure, appropriate systemic anticoagulation according to IFU requirements (e.g., ACT  $\geq$  250 sec). Hospital protocol driven or physician discretion driven use of short acting antihypertensive medications are permitted to control hypertension in order to mitigate bleeding from the arterial access site during the periprocedural period.

An aortogram and selective renal angiography will be performed with all subjects to confirm eligible renal artery anatomy. Ensure subject received a minimum aspirin dose of 250 mg intravenous or up to 325 mg oral (per local drug dose labelling) prior to procedure (unless subject is already taking aspirin on regular basis). If the subject is already taking aspirin daily then at least the usual daily dose should be given on the day of the procedure. If the subject has a documented allergy to aspirin, 75 mg per day of clopidogrel can be substituted; under these circumstances, a loading dose of at least 150 mg clopidogrel may be administered prior to the procedure per physician discretion.

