#### ***9.1.6. Follow -up Visits***

See **Table 3** for details on follow-up visit window and modality requirements for follow-up visits. See **Table 4** and **section 9.1.9** for escape subject requirements. Subjects will return for follow-up visits at 2 weeks, 1 month, 6 weeks, 8 weeks (non-escape only), 10 weeks, 3 months, 6 months, and 12 months post-procedure. Additionally, a 1 month and 4 month post-procedure in-office follow up is required for subjects with a systolic OBP >140 at the 3-month follow-up visit (see **section 9.1.10**).

Follow-up procedures for subjects treated are listed below and must be performed through 12 months follow up for each subject unless otherwise specified. After completion of the study required follow ups, the subjects will return to receiving standard of care follow up.

- **Clinical assessment** will be conducted at the 2 week, 1 and 3-months post-procedure follow-up visit to evaluate the subject's current medical condition. At 4, 6, and 12-months follow up an abbreviated clinical assessment of weight only is required.
- **Office blood pressure** measurements will be obtained in accordance with guidelines in **Appendix 16.5** at all follow-up visits.

- **Laboratory tests** are required at 1, 3, 6, and 12-month follow-up visits:
  - **Basic metabolic panel Chem-7 (blood)**: serum-creatinine, sodium, potassium, blood urea nitrogen (BUN) or urea, bicarbonate, chloride, and glucose. Bicarbonate will not be measured for subjects enrolled in Europe.
  - **eGFR** will be calculated from the serum-creatinine in the Chem-7 panel for eligibility criteria by using the 4 variable Modification of Diet in Renal Disease (MDRD) Formula.
- **Medication and adverse event reviews** will be completed at each follow-up visit to assess any changes in medication usage or medical condition:
  - Enrollment (consent) to 6-months follow up: all medications and all adverse events
  - After 6-months follow up to 12-months follow up: all medications and all serious adverse events

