## 11. Adverse Events and Device Deficiencies

### 11.1. Definitions/Classifications

For each reported adverse event, the Investigator will assess the events in terms of relationship to the device, relationship to the procedure and relationship to the renal denervation therapy (if applicable) as defined below:

- **Device:** A device related AE is defined as any AE for which a causal relationship between the event and the Symplicity Spyral catheter or Symplicity G3 generator can be established.
- **Procedure:** A procedure related AE is defined as any AE occurring within seven days post-procedure associated with the renal angiogram and intervention techniques involved in preparing for the actual renal denervation treatment.
- **Therapy:** A therapy related AE is defined as any AE associated with a subject's physiological response to the renal denervation procedure.

For the purposes of the clinical report, Medtronic will classify each adverse event according to International Organization of Standardization (ISO) ISO 14155:2020.

Where the definition indicates "device", it refers to any device used in the study. This might be the device under investigation, or any market released component of the system. This does not apply to the OBP or ABPM devices used within the study.

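### Subjects found ineligible at the study angiogram have no stated follow-up and no required contact after discharge, so complications that appear later have no planned capture

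*Protocol*

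**What the plan says.** **Eligibility is still open when the artery is entered.** Protocol 9.1.5.1: "The denervation procedure will occur once all eligibility criteria have been met as evaluated at Screening Visit 2 and during the renal angiogram". The same section adds: "An aortogram and selective renal angiography will be performed with all subjects to confirm eligible renal artery anatomy". Section 5 lists this angiogram among the procedures outside standard of care.

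**Exit and follow-up.** Protocol Table 5 has three rows. The first is "Subject enrolled (Patient Information and Informed Consent form signed), but the procedure is never attempted", with follow-up given as None. The second covers death or withdrawal, with follow-up to that point or the last completed visit. The third is "Subject enrolled, undergoes renal denervation and completes the study requirements", with at least 12 months. Section 9.1.6 opens its list with "Follow-up procedures for subjects treated are listed below". Section 9.1.4 has an exit rule for subjects not eligible to go on to the angiogram. There is no matching rule for subjects who fail during it.

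**Adverse events.** Protocol 11.1 counts as procedure-related "any AE occurring within seven days post-procedure associated with the renal angiogram" and the preparatory intervention techniques. Sections 9.2 and 11.2 start adverse event collection at consent, and 11.2 ends it at study termination or exit. Section 9.1.5.4 provides an overnight stay, blood samples and an adverse event assessment before discharge.

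**Analysis.** Protocol 13.2.1 and 13.5, with SAP 7.1.3.1 and 7.7.1, report safety in the ITT population, defined as all enrolled subjects.

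**The concern.** The plan creates a group it does not then describe: people who receive arterial access, anticoagulation and contrast because the study requires it, and who leave without ablation. Protocol 10.1 lists embolism, pseudoaneurysm, retroperitoneal bleeding, dissection and contrast nephropathy among the risks of catheterisation, angiogram included. Some of these can first show themselves after an overnight stay. If nobody is required to contact the subject after discharge, the sponsor learns of such an event only if the subject or a treating physician volunteers it. At stake is the completeness of the safety record for an invasive step done for the study, in a trial so small that one event changes the reported result from zero to non-zero.

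**Working it through.** The documents state no figure to reproduce, so the check sets the sections side by side and then gives a sense of scale.

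**1. Can a subject be catheterised and then fail?** Yes. The schedule (Tables 1 and 3) requires no renal imaging before the procedure visit. Exclusion 4 (FMD) is defined by its angiographic appearance, and 9.1.5.1 leaves eligibility open until the angiogram.

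**2. Which Table 5 row applies?** The term *procedure* is not defined there.
- If it means denervation, row 1 applies and follow-up is None.
- If it means the Procedure Visit (9.1.5, which includes angiography), row 1 does not apply, and row 3 requires denervation.
- Row 2 concerns death or withdrawal. Even if stretched to fit, it ends at withdrawal or the last visit.

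No reading produces a contact after discharge.

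**3. What is collected, and until when?**

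| Period | Provision | Covered? |
|---|---|---|
| Procedure to discharge | 9.1.5.4; event review at procedure and discharge in Table 1 | Yes |
| Events ongoing at exit | 9.6.1 | Yes, status sought |
| First appearing after discharge | 9.1.6 applies to treated subjects; no exit date is set | No planned contact |

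The third period overlaps the seven-day window in 11.1 and the seven-day transfusion criterion for vascular complications in 16.4.

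**4. What does the SAP denominator do?** SAP 7.7.1 keeps a subject who has an adjudicated event before the time of interest, or whose last contact is beyond the lower window. An angiogram-only subject with a captured event therefore counts. One who is event-free and leaves at discharge drops out. One whose event appeared after discharge and was never learned of also drops out, as if event-free.

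**5. Scale.** About 350 − 50 = 300 enrolled subjects are expected not to be treated. The documents do not say how many of them reach angiography. With an assumed failure share *f* among those catheterised:

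- catheterised = 50 / (1 − *f*), rounded up; angiogram-only *m* = catheterised − 50
- chance of at least one complication = 1 − (1 − *p*)^*m*, with an assumed complication rate *p*

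| *f* | Catheterised | *m* | *p* = 2% | *p* = 5% |
|---|---|---|---|---|
| 5% | 52.6 → 53 | 3 | 6% | 14% |
| 10% | 55.6 → 56 | 6 | 11% | 27% |
| 20% | 62.5 → 63 | 13 | 23% | 49% |

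The last two columns cover complications at any time. The share first appearing after discharge is unknown, so the chance of a missed event is lower.

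**6. Effect of one event.** Assume 50 treated subjects, all event-free with complete contact, and one event in an angiogram-only subject. Not captured: 0/50. Captured, under the SAP rule: 1/51 = 2.0%. Over all catheterised subjects when *m* = 13: 1/63 = 1.6%.

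**The case against.** Three stronger readings are tempting, and the documents do not support them.

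*That Table 5 assigns these subjects no follow-up.* This is an inference. Angiography is the first part of the Procedure Visit, 10.1 speaks of the catheterisation procedure as including the angiogram, and 11.1 treats angiogram-related events as procedure-related. A catheterised subject could fairly be said to have had the procedure attempted. The table is ambiguous or silent.

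*That their complications go uncollected.* Events on the table, overnight or present at discharge are collected, and the status of ongoing events is sought at exit. Section 14.1 also has monitors review available source documents for potential adverse events. One reservation remains: 9.1.5.4 describes the stay as following both the angiogram and the procedure, which could be read as treated subjects only, although it says all subjects.

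*That the SAP denominator hides events.* It does not. Any adjudicated event is retained whatever the last contact date, and dropping event-free early leavers raises the rate (1/51 against 1/63). The loss arises at collection.

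It is also fair that no exit date is stated for these subjects, so a site could keep one in the study longer, and that safety is descriptive without a comparator. Both points narrow the concern. Neither supplies a required contact after discharge.

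**Conclusion.** The gap is real and limited. The protocol does not provide for a subject who has arterial access and the study angiogram and is then found ineligible. Events up to discharge or exit are collected. Complications first appearing after discharge have no planned capture, even within the protocol's own seven-day window, although the safety analysis covers all enrolled subjects. The number of people is not in the documents; an assumed angiographic failure share of 5% to 20% gives about 3 to 13. The complication rates used above are also assumptions, and no number of missed events can be derived. This is an inexpensive improvement to data collection and does not undermine the efficacy comparison.

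**What to change.** - **Protocol Table 5:** add a row for arterial access or angiogram performed with no RF energy delivered. Require adverse events and vital status by at least one contact, phone allowed, covering at least the seven-day window. One month is a sensible example: by the SAP's own rule (day 166 for 6 months), the 1-month lower window is day 23, so a contact only at day 7 would leave event-free subjects out of the 1-month denominator.
- **Exit:** state that these subjects are not exited before that contact, and define day zero for them, for example the date of arterial access.
- **Reconcile** 9.1.4, 9.1.5.4, 9.1.6, 11.1 and Table 5. The exit cross-reference in 9.1.4 points to 9.5.1 (investigator reporting), while exit is now in 9.6.1.
- **SAP 7.7.1:** list the number of these subjects and their events separately from treated subjects.

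The cost is protocol and SAP wording, about one phone contact per such subject, and one extra listing. A phone contact will not detect creatinine-based events, and the listing should say so.
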